5.7. Analyses of Efficacy Data

The efficacy variables will be summarized for all patients in FAS. The continuous efficacy variables will be summarized using number of patients, mean, SD, median, Q1, Q3, minimum and maximum. Categorical efficacy variables will be summarized using patient counts and percentage. No formal statistical hypothesis testing will be performed. The graph of mean value for continuous variable or proportion for categorical variable by visit will be provided.

Unless otherwise specified, all observed values, regardless of whether data is collected after withdrawal from study treatment will be used for analysis.

Unless otherwise specified, for the categorical efficacy variables, the proportion of patients with each response at each visit will be calculated using the number of patients with a non-missing value at the visit as the denominator.

Subgroup analyses for efficacy

Different subgroups within the FAS population will be defined as below. The analyses will be performed for the primary efficacy variables by:

- Duration of AD (<5 years, \geq 5 years)
- Baseline weight with grouping (\geq 60kg, <60kg for adolescents, <60 kg, \geq 60-<90 kg, \geq 90 kg for adults)
- BMI with grouping (<35, \geq 35-<40, \geq 40)
- Age (\geq 12-<18, \geq 18-<40, \geq 40-<65, \geq 65)
- Sex (Male, Female)
- Race (Black or African American, Asian, Others)
- Fitzpatrick Skin Types phototype (FST 4; FST 5 + 6 [combined])

5.7.1. Analysis of Primary Efficacy Endpoint (EASI-75)

Primary analyses:

All observed data, regardless of whether rescue treatment is used, or data is collected after study drug withdrawal, will be used to analyze the primary endpoint. Percent of patients achieving EASI-75 at week 24 will be reported. The numerator is the number of patients who achieving EASI-75 at week 24, and the denominator is the number of patients who completed assessment EASI at week 24. Patients with missing data will not be imputed as non-responders. The primary efficacy analyses will be performed on FAS.

Sensitivity analyses:

1. Last observation carried forward – non-responder imputation (LOCF-NRI) approach:

For patients with missing data at week 24 who completed at least 16 weeks of treatment, missing data will be imputed by LOCF from either week 16 or week 20. Patients who received rescue therapy after week 16 will be considered non-responders.

2. Multiple imputation (MI) approach:

Efficacy data through week 24 after rescue medication use will be set to missing first. Missing data will be imputed by MI for 20 times based on patients who have non-missing data. The imputed week 24 EASI will determine EASI-75 response status.

Missing data from the FAS will be imputed 20 times to generate 20 complete data sets by using the SAS procedure MI following the 2 steps below:

Step 1: The monotone missing pattern is induced by Markov Chain Monte Carlo (MCMC) method in SAS procedure MI. The monotone missing pattern means that if a patient has missing value for a variable at a visit, then the values at all subsequent visits for the same variable are all missing for the patient.

Step 2: The missing data at subsequent visits will be imputed using the regression method for the monotone pattern with adjustment for covariates disease severity, and relevant baseline covariates.

The imputation model will include:

- The covariates included the EASI baseline value, the disease severity [IGA 3 vs IGA 4] and measured endpoint values from every clinic visit up to week 24

Week 24 data for each of the 20 complete datasets will be analyzed for EASI-75 response. The SAS MIANALYZE procedure will be used to generate valid statistical inferences by combining results from the 20 analyses using Rubin's formula.

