4.1.2. Secondary Endpoints

Secondary Efficacy Endpoints:

- Proportion of participants with Investigator's Global Assessment (IGA) = 0 to 1 at each visit from baseline through week 24
- Percent change from baseline in EASI at each visit through week 24
- Absolute change from baseline in EASI at each visit through week 24
- Proportion of participants with EASI-50 ($\geq 50\%$ reduction from baseline in EASI) at each visit through week 24
- Proportion of participants with EASI-75 ($\geq 75\%$ reduction from baseline in EASI) at each visit through week 24
- Proportion of participants with EASI-90 ($\geq 90\%$ reduction from baseline in EASI) at each visit through week 24
- Percent change from baseline in total SCORing AD (SCORAD) and SCORAD component scores at each visit through week 24
- Proportion of participants with SCORAD-50 ($\geq 50\%$ reduction in SCORAD from baseline) at each visit through week 24
- Proportion of participants with improvement (reduction) of weekly average of daily Peak Pruritus (PP) NRS ≥ 3 from baseline at each visit through week 24
- Proportion of participants with improvement (reduction) of weekly average of daily PP NRS ≥ 4 from baseline at each visit through week 24
- Percent change from baseline in weekly average of daily PP NRS at each visit through week 24
- Absolute change from baseline in weekly average of daily PP NRS at each visit through week 24
- Change from baseline in percent BSA at each visit through week 24
- Change from baseline in health-related QOL as measured by Dermatology Life Quality Index (DLQI; age ≥ 16), Children's Dermatology Life Quality Index (CDLQI; age < 16) at each visit through week 24
- Change from baseline in Patient Oriented Eczema Measure (POEM) at each visit through week 24

- Change from baseline in Hospital Anxiety and Depression Scale (HADS) at each visit through week 24
- Change from baseline in Skin Pain NRS (SP NRS) at each visit through week 24
- Change from baseline in weekly average Sleep Quality NRS at each visit through week 24
- Proportion of participants with PGID response as No symptoms at each visit through week 24
- Proportion of participants with PGID response as No symptoms or Mild symptoms at each visit through week 24
- Proportion of participants who rate their eczema symptoms in PGIC as “Much better” at each visit through week 24
- Proportion of participants who rate their eczema symptoms in PGIC as “Much better” or “Moderately better” at each visit through week 24

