11.4.3. Efficacy Analyses

11.4.3.1. Primary Efficacy Analysis

The primary endpoint will be summarized descriptively with no hypothesis testing planned. Subgroup analysis will be performed. Details will be specified in the SAP.

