11.4.3.2. Secondary Efficacy Analysis

For continuous variables, descriptive statistics will include the following information: number of participants reflected in the calculation (n), mean, median, 25% percentile, 75% percentile, 75% percentile, standard deviation, minimum and maximum.

For categorical or ordinal data, frequencies and percentages will be displayed for each category.

Primary Imputation Method:

- For continuous endpoints: Data after rescue or drop-out due to lack of efficacy, will be assigned by post baseline last-observation carried forward (LOCF); MI will be applied for all other missing data.
- Binary/responder endpoints will be calculated based on the corresponding continuous assessments (based on the values after imputation)

Other sensitivity analyses with different imputation methods will be planned and detailed in the study SAP.

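### Efficacy data after rescue fall under conflicting rules, so week-24 EASI-75 can take more than one value; the primary rate is an observed-case rate under an FAS label, and the FAS differs between documents

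*SAP*

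**What the plan says.** **Rescue.** The first sentence of Protocol 8.3 says that, for participants given rescue, the efficacy results actually observed are analysed. Its last sentence counts the same participants as treatment failures in the efficacy analysis. For the primary endpoint, SAP 5.7.1 uses "All observed data, regardless of whether rescue treatment is used".

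**Secondary endpoints.** Protocol 11.4.3.2, under its Primary Imputation Method, says of continuous endpoints: "Data after rescue or drop-out due to lack of efficacy, will be assigned by post baseline last-observation carried forward (LOCF"), with MI for all other missing data. It adds: "Binary/responder endpoints will be calculated based on the corresponding continuous assessments (based on the values after imputation"). The secondary endpoints in Protocol 4.1.2 include "Proportion of participants with EASI-75" at each visit through week 24. SAP 5.7 and 5.7.2 instead use all observed data and, for categorical variables, divide by those with a value at the visit.

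**Primary denominator.** Protocol 11.4.3.1 gives no missing-data rule for the primary endpoint and says "Details will be specified in the SAP". SAP 5.7.1 says "The primary efficacy analyses will be performed on FAS", but also "the denominator is the number of patients who completed assessment EASI at week 24. Patients with missing data will not be imputed as non-responders". Its MI sensitivity analysis first sets post-rescue efficacy data to missing; then "Missing data from the FAS will be imputed 20 times to generate 20 complete data sets".

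**Analysis sets.** Protocol 11.3.1 requires at least one efficacy assessment after baseline for the FAS; SAP 3.1 requires only a baseline assessment. Both documents (Protocol 11.3.2, SAP 3.2) define the SAF as a subset of the FAS.

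**The concern.** With one arm and no test, the EASI-75 proportion is itself the result, so the rules that decide who is a responder and who is counted must be unambiguous.

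A rescued participant with a good week-24 EASI is a responder under one sentence of Protocol 8.3 and a failure under another. Week-24 EASI-75 is both the primary endpoint and one time point of a secondary endpoint, and the rules for the two roles differ. A rate labelled FAS that leaves out FAS members without a week-24 EASI equals the FAS rate only if missingness is unrelated to response. Two FAS definitions mean two possible populations for the same table, and nesting the SAF carries that difference into safety.

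**Working it through.** **Inputs.** From the documents: up to 120 participants and up to 15% dropout, said to leave approximately 105 (Protocol 11.2). They give no response or rescue rate. The counts below are assumptions, with an FAS of 120 and every dropout lacking a week-24 EASI.

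**The plan's own figure.** 120 × 0.85 = 102, against the stated approximate 105. Exactly 105 of 120 implies 1 − 105/120 = 12.5% dropout. Both are carried below.

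**(a) Rescue rule, primary endpoint.** Take 71/102 = 69.6% under the observed rule. Under the treatment-failure rule, rescued responders leave the numerator, so the gap is (rescued responders)/102:

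- 5 rescued, 2 responding: 2/102 = 2.0 points.
- 10 rescued, 5 responding: (71 − 5)/102 = 66/102 = 64.7%, a gap of 4.9 points.
- 20 rescued, 10 responding: 10/102 = 9.8 points.
- No rescued participant responding: 0.

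**(b) Secondary rule, week-24 EASI-75.** Under Protocol 11.4.3.2 a rescued participant's week-24 status comes from the last observation before rescue. If 1 of the 10 rescued met EASI-75 at that visit, the rate is (71 − 5 + 1)/102 = 67/102 = 65.7%, against 69.6% under SAP 5.7.1. The denominator is held at 102 to isolate the rescue effect; MI for the other missing values would move it further. The SAP 5.7.2 table does not list EASI-75, but SAP 4.4.2 names it as secondary and the general denominator rule in SAP 5.7 covers it.

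**(c) Denominator.** Full-FAS rate = (observed responders + number missing × response rate in the missing)/120. For 102 assessed and half the observed rate: (71 + 18 × 0.348)/120 = 64.4%. All scenarios:

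| Assessed of 120 | Observed rate | Missing respond equally | At half the rate | None respond | At 1.2 times the rate |
|---|---|---|---|---|---|
| 102 | 71/102 = 69.6% | 69.6% | 64.4% | 59.2% | 71.7% |
| 105 | 73/105 = 69.5% | 69.5% | 65.2% | 60.8% | 71.3% |
| 114 | 80/114 = 70.2% | 70.2% | 68.4% | 66.7% | 70.9% |

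For scale, the exact 95% interval for 71/102 is 59.7% to 78.3%.

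The planned sensitivity analyses do not supply the missing figure. The MI removes post-rescue data before imputing, so it changes the rescue rule and the missing-data rule together. The LOCF-NRI analysis treats rescue after week 16 as non-response and states no rule for participants missing week 24 with under 16 weeks of treatment. No planned analysis therefore gives the full-FAS rate under the primary's own observed-data rule.

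**(d) Analysis sets.** A dosed participant with a baseline assessment but no later efficacy assessment is outside the protocol FAS, and so outside the protocol SAF. Under SAP 3.1 and 3.2 the same participant is in both.

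**The case against.** The strongest reply concerns the denominator. The study is descriptive, the SAP states its rule in plain words, the protocol delegates the detail, and an MI analysis over the FAS is already planned. An observed-case proportion is a common descriptive summary. All of this stands. A reader might infer that SAP 5.7.1 breaches the protocol; it does not, because the LOCF/MI rule sits under the secondary analysis. What remains is a label that does not match the denominator, and a cheap improvement.

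A reader might also infer that the completer rate is inflated. The documents do not show this. The gap depends on how the missing would have responded and can be zero or negative. Protocol 8.4.2 and 9.1.2 ask participants who stop treatment or withdraw to return, so fewer than 15% may be missing.

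Nor is the rescue conflict three-way for the primary endpoint. It is observed against treatment failure; LOCF enters only through the secondary by-visit EASI-75.

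On safety, the SAP's version of the SAF loses almost no one, since baseline disease scores are needed for eligibility. The loss arises under the protocol's definition.

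The reply does not answer the contradiction within Protocol 8.3, the unexplained departure from Protocol 11.4.3.2, or the two FAS definitions.

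**Conclusion.** The point holds in four parts, and the sponsor should act on it. Parts (a), (b) and (d) are conflicts in the current text and rest on no assumption:

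- **(a)** Protocol 8.3 gives opposite rules for a rescued participant, and the SAP follows one without acknowledging the other.
- **(b)** The SAP replaces the protocol's imputation method for all secondary endpoints without explanation, which leaves week-24 EASI-75 with two possible values.
- **(d)** The FAS definitions differ, and the protocol's nested SAF can lose dosed participants from safety.
- **(c)** The primary rate is an observed-case rate under an FAS label. This is a matter of labelling and of the choice of primary estimate, not a protocol breach.

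Only the sizes are illustrative, since the response and rescue rates are assumed. In those scenarios the rescue choice moves the rate by 0 to 9.8 points. At 15% missing, the full-FAS rate lies between 10.4 points below and 2.1 points above the observed rate. The direction of any bias is not established. No test is planned, so error rates are not affected.

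**What to change.** 1. Reconcile the two sentences of Protocol 8.3 with SAP 5.7.1 for the primary endpoint, and with Protocol 11.4.3.2 and SAP 5.7.2 for the secondary endpoints. Set one analysis rule for post-rescue efficacy data per endpoint class. Which rule is for the sponsor to decide, but week-24 EASI-75 must have one value. State whether post-rescue values enter the imputation model.
2. In SAP 5.7.1, make the primary estimate week-24 EASI-75 over all FAS participants, using the MI model already specified and the reconciled post-rescue rule. Keep the current rate as supportive, labelled as observed cases, with the number missing by reason.
3. For every secondary endpoint that Protocol 11.4.3.2 covers, either apply that section as reconciled or amend it to observed cases and label the results so. This includes the continuous endpoints (EASI, SCORAD, PP NRS, BSA, DLQI/CDLQI, POEM, HADS, Skin Pain, Sleep Quality) as well as the responder endpoints. State how IGA, PGID and PGIC are handled: the section covers responder endpoints without exception, yet relies on a corresponding continuous assessment.
4. Use one FAS definition in both documents, and define the SAF as all participants who received at least one dose, not as a subset of the FAS.

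**Cost.** A SAP amendment and protocol wording. The primary needs little new programming, because MI for EASI over the FAS is already planned. Keeping Protocol 11.4.3.2 requires MI models for every covered secondary endpoint; amending it requires labels only. The headline rate becomes model-based and may be lower, unchanged or slightly higher.

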8.3. Rescue Treatments

For participants who receive rescue treatment during treatment period, observed efficacy results will be analyzed in this study.

If medically necessary (ie, to control intolerable AD symptoms), rescue treatment for AD may be provided to study participants at the discretion of the investigator. Although the use of rescue medications is allowed at any time during the study, the use of rescue medications should be delayed, if possible, for at least 14 days following the initiation of the investigational treatment. If possible, investigators are encouraged to consider rescue initially with topical treatment (eg, medium/high potency TCS) and to escalate to systemic medications only for participants who do not respond adequately after at least 7 days of topical treatment. Topical calcineurin inhibitors may be used for rescue, alone or in combination with TCS, but the use of TCI should be reserved for problem areas only (eg, face, neck, intertriginous and genital areas, etc). Investigators may also consider rescue with crisaborole. Rescue treatment for these topical therapies should be used as per prescribing information and local guidelines. Participants may continue study treatment if rescue consists of topical medications.

Participants who receive systemic corticosteroids or systemic nonsteroidal immunosuppressive drugs (eg, cyclosporine, methotrexate, mycophenolate mofetil, azathioprine, etc) as rescue medication during the study will be discontinued permanently from the study drug. All participants will be asked to complete the scheduled study visits and assessments whether or not they complete study treatment and whether or not they receive rescue treatment for AD. Investigators should make every attempt to conduct efficacy and safety assessments (eg, disease severity scores, safety laboratory tests) before administering any rescue treatment. An unscheduled visit may be used for this purpose, if necessary. For the purpose of efficacy analysis, participants who receive rescue treatment during the study will be considered treatment failures.

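### The LOCF-NRI sensitivity analysis fails rescue only after week 16, so no analysis specified in the SAP implements the protocol's rescue-as-failure sentence

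*SAP*

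**What the plan says.** SAP 5.7.1 specifies three analyses of EASI-75 at week 24.

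- **Primary:** "All observed data, regardless of whether rescue treatment is used, or data is collected after study drug withdrawal, will be used". Missing values are not imputed, and the denominator is participants with a week-24 EASI.
- **Sensitivity 1 (LOCF-NRI):** "For patients with missing data at week 24 who completed at least 16 weeks of treatment, missing data will be imputed by LOCF", taken from week 16 or week 20. The next sentence is "Patients who received rescue therapy after week 16 will be considered non-responders". The rule ends there, and no reason is given for the week-16 cut.
- **Sensitivity 2 (MI):** "Efficacy data through week 24 after rescue medication use will be set to missing first". The gaps are then multiply imputed.

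SAP 5.7.2 uses observed values for the secondary endpoints whether or not rescue was used. Unless another rule is stated, SAP 5.7 calculates visit proportions "using the number of patients with a non-missing value at the visit as the denominator".

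Protocol 8.3 opens with "For participants who receive rescue treatment during treatment period, observed efficacy results will be analyzed in this study" and closes with "For the purpose of efficacy analysis, participants who receive rescue treatment during the study will be considered treatment failures". On timing it says: "Although the use of rescue medications is allowed at any time during the study". Study treatment may continue after topical rescue. Systemic rescue ends study drug, but everyone is asked to keep attending visits.

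Protocol 11.4.3.2, under secondary efficacy, gives a third rule (LOCF after rescue). It also lets the SAP add sensitivity analyses with other imputation methods.

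**The concern.** The study is single-arm and descriptive, so the reported percentage is the result. The primary analysis keeps post-rescue values and drops participants with no week-24 EASI. Sensitivity 1 is the only specified analysis that treats any rescue as failure, and its label promises non-responder imputation. A reader who wants a stricter figure will look there.

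As written, it can still credit a participant rescued in the first 16 weeks with a response that may partly reflect the rescue treatment. Its numerator and denominator also depend on readings that the SAP does not settle, so two programmers could both follow the text and report different percentages.

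**Working it through.** **1. The plan's own figure.** Protocol 11.2 gives 120 participants, up to 15% dropout and about 105 remaining. 120 × (1 − 0.15) = 102, close to the stated 105 (which corresponds to 15/120 = 12.5%). That leaves 15 to 18 participants without week-24 data. The number is itself uncertain, because Protocol 9.1.2 asks withdrawn participants back for week 24. The point does not depend on it.

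**2. How rescue at or before week 16 is handled.**

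| Rule | Handling |
|---|---|
| SAP primary | observed value counts |
| SAP sensitivity 1 | observed value counts, or a week-16/20 value is carried forward; no stated rule if week 24 is missing with under 16 weeks of treatment |
| SAP sensitivity 2 | post-rescue values removed, then imputed |
| SAP secondary endpoints | observed value counts |
| Protocol 8.3, opening sentence | observed value counts |
| Protocol 8.3, closing sentence | failure, no time limit |
| Protocol 11.4.3.2 | LOCF after rescue |

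No SAP row assigns failure. The week-16 cut matches none of the three protocol rules.

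**3. Routes to response after early rescue.** (a) An observed week-24 value, after topical or systemic rescue, because visits continue. (b) A carried-forward week-16 or week-20 value, mainly after topical rescue, because study treatment can continue.

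**4. Can systemic rescue near week 16 take route (b)?** The 16-week treatment condition is not defined, and the exposure formulas differ. For a last dose at week 14:

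- Protocol 11.4.5.3: 98 + 14 = 112 days, exactly 16 weeks, so the condition is met.
- SAP 5.6: 98 + 7 = 105 days, 15 weeks, so it is not met.

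Eligibility for LOCF therefore depends on which formula is used.

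**5. Value of one participant.** With a denominator of 120, each early-rescued responder reclassified moves the estimate by 1/120 = 0.83 points. For 0, 2, 5 or 10 such participants (assumed) the change is 0, 1.7, 4.2 or 8.3 points.

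**6. Illustration.** All inputs except 120 and 105 are assumed. R = 73 of 105 respond at week 24, so the primary is 73/105 = 69.5%. Of the 15 missing, E = 10 had under 16 weeks of treatment and C = 2 of the other 5 respond by LOCF. L = 2 observed responders were rescued after week 16. B = 5 counted responders were rescued by week 16. No carried-forward responder was rescued late.

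| Reading of sensitivity 1 | Formula | Result |
|---|---|---|
| Rescue sentence covers all FAS; early dropouts fail | (R − L + C)/120 = 73/120 | 60.8% |
| Rescue sentence limited to carried-forward; early dropouts fail | (R + C)/120 = 75/120 | 62.5% |
| Rescue sentence covers all FAS; early dropouts left out | (R − L + C)/110 = 73/110 | 66.4% |
| Rescue at any time fails; early dropouts fail | (R − L + C − B)/120 = 68/120 | 56.7% |

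The gap between leaving early dropouts out and failing them varies with E. It is 0 points at E = 0 (C = 7), 2.8 at E = 5 (C = 5; 76/115 against 76/120), 5.5 at E = 10 and 8.5 at E = 15 (C = 0; 71/105 against 71/120).

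**7. Direction.** With L = 0, C = 5 and E = 10, leaving early dropouts out gives 78/110 = 70.9%, above the primary; failing them gives 78/120 = 65.0%, below it.

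**8. FAS.** Protocol 11.3.1 requires a post-baseline efficacy assessment; SAP 3.1 requires only a baseline assessment. If 0, 2 or 5 participants (assumed) have no post-baseline assessment, 73 responders give 73/120 = 60.8%, 73/118 = 61.9% or 73/115 = 63.5% under the protocol definition, against 60.8% under the SAP's.

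**The case against.** **Early rescue is already examined.** The MI analysis removes every post-rescue value whatever its timing, the primary follows the opening sentence of Protocol 8.3, and Protocol 11.4.3.2 allows different sensitivity rules. All of this stands. A reader might infer that early rescue is ignored throughout, or that the SAP breaches the protocol; the documents support neither. What remains is narrower: MI imputes rather than fails, the closing sentence of Protocol 8.3 has no counterpart in any specified analysis, and the week-16 cut is unexplained.

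**The sentence may only guard the LOCF step.** It directly follows the carry-forward rule, and week 16 is where that window starts, so it may only stop a value being carried past later rescue. This is plausible and the text does not rule it out. But then no participant with an observed week-24 value fails for rescue at any time, and a week-16 value obtained after earlier topical rescue is still carried forward.

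**The NRI label already settles early dropouts.** It does suggest non-response, which is the more natural reading. No sentence says so, however, and the SAP 5.7 default would leave them out.

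**The sizes are assumed.** Correct. A reader might infer that the analysis must overstate response, or that ambiguous wording alone decides whether it falls above or below the primary. Neither follows. With no rescue, no early dropouts and all 15 missing participants responding by LOCF, every reading gives 88/120 = 73.3% against 69.5%, and so would the corrected rule.

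**Systemic rescue by week 16 cannot be carried forward.** A reader might assume this because study drug stops. Step 4 shows that it depends on the exposure formula.

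**Conclusion.** The point holds for the analyses the SAP specifies. Sensitivity 1 fails rescue only after week 16, so none of them implements the closing sentence of Protocol 8.3, and a participant rescued by week 16 can be counted as an EASI-75 responder. It would go too far to say that the plan has no rescue-as-failure rule: Protocol 8.3 states one, and sensitivity 1 applies it to late rescue.

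Three things also remain unsettled: the scope of the rescue sentence, the handling of participants with under 16 weeks of treatment and no week-24 value, and the meaning of the 16-week condition.

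Size and direction are unknown. The only firm figure is 0.83 points per reclassified participant, which assumes a denominator of 120. The 56.7% to 66.4% spread illustrates how far the rule can matter on the same data; it is not an estimate. The primary result is unaffected, but the text should be corrected because this is its only check that fails any rescue.

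**What to change.** For sensitivity analysis 1 only:

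1. Use the FAS as denominator, under one definition in both documents.
2. Count any rescue before the week-24 assessment as non-response, for all FAS participants and whatever its timing.
3. Apply LOCF from week 16 or week 20 only to unrescued participants who lack a week-24 value and meet the 16-week treatment condition, defined by one exposure rule.
4. Count every other missing week-24 value as non-response.

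Keep the primary and MI analyses as they are. Reconcile how rescue is handled in the analysis across the two sentences in Protocol 8.3, Protocol 11.4.3.2 and SAP 5.7.1. This concerns analysis only, not who may receive rescue or when.

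The cost is a few SAP sentences, alignment of the protocol text and minor reprogramming, with no new data. The downside is that the sensitivity estimate may be less favourable.
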